Cover page

Official title of the study:

BCG to Reduce Absenteeism Among Health Care Workers During the COVID-19 Pandemic

NCT number:

NCT04641858 - <https://clinicaltrials.gov/ct2/show/NCT04641858>

Date of document:

January 20, 2022

BCG vaccine to reduce unplanned absenteeism due to illness of health care workers during the COVID-19 pandemic. A multi-center randomised controlled trial (BCG-COVID-RCT)

LIST OF ABBREVIATIONS

AEs – Adverse Events

BCG – Bacille Calmette-Guérin

CFU – Colony-Forming Units

CI – Confidence Interval

COVID-19 – Corona Virus Disease

DSMB – Data Safety and Management Board

EDCTP - European & Developing Countries Clinical Trials Partnership

HCW – Health Care Workers

HIV – Human Immunodeficiency virus

ISC – International Steering Committee

NSC – National Steering Committee

NSEs – Non-specific effects

PCR – Polymerase Chain Reaction

POC – Point Of Care

PI – Principal Investigator

RCT – Randomized Controlled Trial

RR – Relative Risk

SAEs – Serious Adverse Events

SARS-CoV2 - Severe Acute Respiratory Syndrome Coronavirus 2

ABSTRACT

The COVID-19 pandemic challenges available hospital capacity. This is augmented by absenteeism of health care workers (HCW). Strategies to protect HCW are desperately needed. Bacille Calmette-Guérin (BCG) has protective non-specific effects against other infections; a plausible immunological mechanism has been identified in terms of "trained innate immunity". European and North American trials to study if BCG can reduce the incidence and/or severity of COVID-19 have now been initiated. African studies are needed. The underlying hypothesis for this study is that BCG vaccination of HCW reduces unplanned absenteeism due to illness by 20%.

The primary objective of the study is to evaluate whether BCG can reduce unplanned absenteeism due to illness among HCW during the COVID-19 pandemic. Secondary objectives are to reduce the number of HCW that are infected with COVID-19, reduce hospital admissions of HCW during the COVID-19 pandemic and to improve the capacity for clinical research in Cape Verde and Guinea-Bissau.

Design: Single-blind, parallel-group placebo-controlled multi-centre block randomized trial including a total of 1050 HCW. The study sites will be the Manhiça District Hospital and Mavalane Hospital in Mozambique and Hospital Nacional Simão Mendes and other hospitals in the capital Bissau in Guinea-Bissau. Population: HCW (nurses/physicians/others) ≥ 18 years. Exclusion criteria: known allergy to (components of) BCG or serious adverse events to prior BCG administration; known previous, active or latent infection with Mycobacterium tuberculosis or other mycobacterial species, fever (>38 C) within past 24 hours; suspicion of active viral or bacterial infection, severely immunocompromised subjects, self-reported HIV infection, self-reported pregnancy; active solid or non-solid malignancy or lymphoma within the last two years; any other contraindications for live-attenuated vaccine administration fulfilled, not having a mobile phone.

Intervention: Block randomization 1:1 to intradermal standard dose (0.1 ml) of BCG vaccine or placebo (saline). Endpoints: Primary: Days of unplanned absenteeism due to illness. Secondary: Days of absenteeism because of documented COVID-19; cumulative incidence of infectious disease hospitalizations.

Baseline data collection: Enrolment data regarding chronic illnesses and treatment, lifestyle (family structure, socioeconomic factors, smoking), vaccination history including previous BCG vaccination. Blood sample for SARS-CoV-2 serology. Follow-up: mobile phone interviews every second week, regarding symptoms, absenteeism and causes, COVID-19 testing (if done) and their results. Supplemented by daily workplace presence registry information (where present).

Statistical analysis: Total number of unplanned days of absenteeism analysed using Bayesian negative binomial regression with a fixed effect for BCG, hospital, professional category, observation week, number of average workdays per week. Monthly interim analyses.

Adaptive design with frequent interim analyses will allow results to inform policy-makers during the ongoing pandemic.

Perspectives: If BCG can reduce HCW absenteeism it has global implications. The intervention can quickly be scaled up all over the world.

ADMINISTRATIVE INFORMATION

Trial registration

The trial is registered at clinicaltrials.gov. (<https://clinicaltrials.gov/ct2/show/NCT04641858>)

Data category	Information
Primary registry and trial identifying number	https://clinicaltrials.gov/ct2/show/NCT04641858
Date of registration in primary registry	November 24, 2020
Secondary identifying numbers	NA
Source(s) of monetary or material support	EDCTP
Primary sponsor	EDCTP
Secondary sponsor(s)	Institute of Hygiene and Tropical Medicine, NOVA University Lisbon University of Southern Denmark
Contact for public queries	[name]
Contact for scientific queries	[name]
Public title	
Scientific title	BCG vaccine to reduce unplanned absenteeism due to illness of health care workers during the COVID-19 pandemic. A multi-centre randomised controlled trial (BCG-COVID-RCT)
Countries of recruitment	Guinea-Bissau, Mozambique
Health condition(s) or problem(s) studied	BCG vaccine, absenteeism, COVID-19
Intervention(s)	Active comparator: intradermal standard 0.1 ml dose of attenuated Mycobacterium bovis BCG (Bacillus Calmette-Guerin), Danish strain 1331, 2-8 × 10 ⁵ CFU Placebo comparator: intradermal standard 0.1 ml saline solution (NaCl 0.9%)
Key inclusion and exclusion criteria	Population: Health care workers (physicians, nurses, and others), ≥ 18 years. Exclusion if known allergy or previous adverse events to BCG; previous/active infection with M. tuberculosis; Fever (> 38 C) within past 24 hours; Suspicion of active viral/bacterial/HIV infection; Pregnancy; Being immunocompromised; Not having mobile phone.
Study type	Single-blind, parallel-group placebo-controlled adaptive multi-centre block-randomised trial including a total of 1050 HCW with two arms (BCG arm and placebo arm).
Date of first enrolment	
Target sample size	1050
Primary outcome(s)	Days of unplanned absenteeism due to illness
Key secondary outcomes	Days of unplanned absenteeism due to documented COVID-19; Cumulative incidence of hospitalisations

Funding

EDCTP is funding the run-in costs for the BCG-COVID-RCT, including trials in the respective countries and for training and management. The budget of each RCT site covers costs related to regulatory and ethical approval, clinical and supervisory personnel, field workers (enrolment of study subjects and data collection, including biological samples), costs of communication, cost of materials (offices, electricity, vaccines) and costs of communication (follow up will be by telephone).

The collaboration of the tenured staff members of the Cape Verdean, Danish and Portuguese Institutions (University of Cape Verde, National Institute of Public Health of Cape Verde, University of Southern Denmark, NOVA University Lisbon, Portugal) will be fully supported by their own institutions.

TECHNICAL INFORMATION

Background and rationale

The COVID-19 pandemic reflects a serious threat to hospital personnel capacity as the number of COVID-19 infected patients that require hospital care may well exceed the capacity of hospital personnel. Furthermore, healthcare workers (HCW) face an elevated risk of exposure to - and infection with - SARS-CoV-2. Even if further mobilisation of hospital personnel is possible to some extent, it is imperative to ensure the safety, health and fitness of hospital personnel, not only for moral and professional reasons, but also in order to safeguard continuous patient care and to prevent health care systems from collapsing. Strategies to prevent COVID-19 infection or to mitigate its clinical consequences among HCW are therefore desperately needed.

To date, treatment therapies for COVID-19 has been of supportive nature, and no curative or protective treatment has been identified yet, despite many ongoing trials. Particularly, there are no interventions specifically targeting HCW, apart from adequate personal protective equipment and sound professional practices.

Bacillus Calmette-Guérin (BCG) was developed as a vaccine against tuberculosis, but it has been shown that it can protect against death from other infections - it has so-called *non-specific effects* (NSEs) (1-3). In clinical studies, BCG vaccination was associated with reduced infant mortality, mainly as a result of fewer cases of neonatal sepsis and respiratory infections (4-6). NSEs of BCG are not limited to infants (7,8). For instance, an Indonesian trial showed that consecutive BCG vaccination for 3 months reduced the incidence of acute upper tract respiratory infections by 80% (95%CI=22% to 95%) (8), and in a South African trial among adolescents, the risk of upper respiratory tract infections was 2.1% in the BCG revaccination group but 7.9% in the placebo group (P<0.001) (9).

It has recently been demonstrated that the beneficial NSEs of BCG vaccination are due to epigenetic and metabolic reprogramming of innate immune cells leading to an increased antimicrobial activity, a process termed "trained immunity" (10). Upon stimulation with a pathogen, the innate immune system becomes primed and can react faster and more efficiently to a secondary (and non-related) stimulus. These effects lasts for at least one year (10). There is proof-of-principle that this will affect the course of a viral challenge; in a human experimental study randomising adult volunteers to BCG vs. placebo 4 weeks prior to a yellow fever vaccine challenge, those who had received BCG had a lower yellow fever viral load, and improved anti-viral responses (11).

Boosting with BCG (revaccination) may enhance these beneficial NSEs (12). This has been shown for children in an RCT of BCG revaccination (13). Also, the therapeutic effect of BCG for bladder cancer is higher for patients that had previously been vaccinated with BCG (14). It was recently demonstrated in a pilot study of 40 Guineans above 50 years of age, that BCG revaccination was associated with "innate training", and this was most pronounced in individuals who had a positive IGRA test (submitted). In the proposed trial, boosting may be important, as many HCW are expected to have been BCG vaccinated previously.

BCG vaccine in immunocompetent adults is considered safe, also for persons with prior BCG vaccination and even in latently infected adults (15). In a randomised controlled trial (RCT) that compared revaccination with BCG versus placebo, no vaccine-related serious adverse events were observed in the 312 patients in the BCG arm (9).

Research hypothesis

The COVID-19 pandemic in Africa challenges available hospital capacity. This is augmented by unplanned absenteeism of HCW. Strategies to prevent their absenteeism are needed. BCG has

protective NSEs against other infections and a plausible immunological mechanism, “trained innate immunity”, has been identified.

Based on the capacity of BCG to: 1) reduce the incidence of respiratory tract infections and mortality in children and perhaps in the elderly; 2) exert antiviral effects and reduce viremia in an experimental human model of viral infection, we hypothesize that BCG vaccination may induce partial protection against susceptibility to and/or severity of COVID-19 and associated complications which might result in a reduction in the number of days of unplanned absenteeism from work for HCW.

[figure not shown]
Objectives

Primary: Test the capability of BCG to reduce absenteeism among HCW working at a health care facility that treats patients who could suffer from COVID during the COVID-19 pandemic. Secondary: reduce number of HCW that develop COVID-19; ii) reduce number of hospital admissions due to illness of HCW during the COVID-19 pandemic; iii) improve capacity for clinical research in Guinea-Bissau.

Trial design

Single-blind, parallel-group placebo-controlled adaptive multi-centre trial, with block-randomisation 1:1 to intradermal standard 0.1 ml dose of BCG vaccine or placebo (saline) including a total of 1050 HCW (BCG arm and placebo arm).

Figure 1 – Trial design and flowchart

Study population

Health Care Workers defined as a person who delivers care and services to the sick and ailing either directly as doctors and nurses or indirectly as aides, helpers, laboratory technicians, or even medical waste handlers.

Inclusion and exclusion criteria for participants

Participants must provide written, informed consent before any study procedures occur (see ethics section).

Inclusion criteria

Participants eligible for the trial must comply with all of the following at randomization:

- health care worker (physician, nurse, or other) based at one of the research hospitals.
- age ≥ 18 years

Exclusion criteria

- known allergy to (components of) BCG or serious adverse events to prior BCG administration;

- known previous, active or latent infection with *Mycobacterium tuberculosis* or other mycobacterial species
- fever (>38 C) within past 24 hours;
- suspicion of active viral or bacterial infection
- severely immunocompromised subjects
- self-reported HIV infection or a positive HIV test at inclusion
- self-reported pregnancy;
- active solid or non-solid malignancy or lymphoma within the prior two years;
- contraindications for live attenuated vaccine administration.
- not having a mobile phone.

Intervention

The intervention will consist of the administration of an intradermal injection of a standard 0.1 ml adult dose of attenuated *Mycobacterium bovis* BCG (Bacillus Calmette-Guerin), Danish strain 1331, $2-8 \times 10^5$ CFU or the placebo comparator: intradermal standard 0.1 ml saline solution (NaCl 0.9%). Both BCG and saline solution will be injected in the skin over the upper deltoid muscle.

Product name	Manufacturer	Details of product
BCG	AJ vaccines (first market authorization 1993 - marketing authorization number 14762)	Attenuated Mycobacterium bovis BCG (Bacillus Calmette-Guerin), Danish strain 1331, $2-8 \times 10^5$ cfu (Approval for use No 08731) http://www.produktresume.dk/AppBuilder/search?utf8=%E2%9C%93&id=&type=&q=bcg&button=S%C3%B8g
Saline Solution (NaCl 0.9%)	NA	NA

The BCG vaccine has been commercialized since the 1930s and the current stock is sufficient to meet the study needs. BCG vaccines from different manufacturers are not identical. The results from this clinical trial will therefore be applicable for BCG Vaccine AJV and not necessarily to other BCG vaccine strains.

The expected local reaction after successful vaccination with BCG Vaccine "AJ Vaccines" is injection site swelling followed by a local lesion that can form an ulcer after 2-4 weeks and heal after a few months, leaving a small flat scar. Redness and tenderness may occur at the injection site. Regional swelling of the lymph node <1 cm may also occur. Not common ($\geq 1/1,000$ to <1/100) and rare ($\geq 1/10,000$ to 1/1,000) adverse reactions:

- Blood and lymphatic system - Regional swelling of lymph nodes > 1 cm
- Nervous system disorders - Headache
- Bones, joints, muscles and connective tissue - Osteitis
- Infections and parasitic diseases - Suppurative lymphadenitis, osteomyelitis, BCGitis
- Abscess at the injection site

We will specifically enquire about adverse events at the biweekly interviews and in the end questionnaire.

Outcomes

Primary outcome measures

Difference between the two treatment arms in the numbers of days of unplanned absenteeism due to illness.

Secondary outcome measures

Days of unplanned absenteeism because of documented COVID-19 and cumulative incidence of hospital admissions due to illness (minus accidents).

Unplanned absenteeism is defined by being absent from work due to causes other than holidays, parental leave, and other planned leaves, family assistance (including mourning leave) and quarantine measures.

Hospital admissions involves staying at a hospital for at least one night or more for medical reasons. It includes admissions to hospital wards and overnight stays in emergency departments.

Sample size

The sample size was calculated on the basis of the primary hypothesis. A total of 1050 HCW randomized with an estimated loss to follow-up of 5%, and a mean number of days off work due to illness in the control group of 5 days (SD=5) over a 6-month period will demonstrate a reduction among BCG vaccinated of 20% for a mean absence of 4 days (80% power and alpha 0.05). The estimated loss to follow-up (5%) was based on past telephone-based surveys conducted in Mozambique and Bissau.

Assignment of interventions

Randomization

All participants who give consent for participation and who fulfil the inclusion criteria will be randomly assigned to either placebo or BCG group with a 1:1 (treatment:placebo) allocation in blocks of 4 to 6 within strata defined by gender (male/female) and occupational group (doctors/nurses/other).

Blinding

The BCG vaccine will be administered by study physicians/nurses, who are not blinded but also not involved in the data collection. Participants, data collectors and data entry clerks will be blinded to the treatment allocation. In case of serious adverse events, the participant can be unblinded after consultation with the investigator or the vaccinating physician/nurse.

When the study has ended, all participants will receive information about the intervention that they received.

Data collection

Data collection instruments include: consent form, inclusion/exclusion criteria form, baseline questionnaire, follow-up questionnaire, and end questionnaire.

Variables

The endpoint variables are described in

Table 1.

Table 1 – Definition of end-point variables

Variables	Definition	Type	Scale	Domain
Absenteeism	Refers to the total number of days absent from work due to illness	Quantitative	Numeric	In days

Variables	Definition	Type	Scale	Domain
Absenteeism for COVID-19	Refers to the number of days absent from work due to COVID-19	Quantitative	Numeric	In days
Absenteeism besides COVID-19	Refers to the number of days absent from work due to diseases /illness besides COVID-19	Quantitative	Numeric	In days
Absenteeism for infections	Refers to the number of days (unplanned) absent from work due to infections	Quantitative	Numeric	In days
Absenteeism for respiratory infections	Refers to the number of days (unplanned) absent from work due to respiratory infections	Quantitative	Numeric	In days
COVID-19 infection	Describes if the participant is positive for SARS-CoV2 or has had COVID-19	Qualitative	Nominal	No Yes
Death	Whether the participant died during follow-up	Qualitative	Nominal	No Yes
Cumulative incidence of infectious disease episodes	Cumulative incidence of infectious disease episodes	Quantitative	Numeric	Episodes
Cumulative incidence of respiratory infectious disease episodes	Cumulative incidence of respiratory infectious disease episodes	Quantitative	Numeric	Episodes
Cumulative incidence of hospital admissions	Cumulative incidence of hospital admissions	Quantitative	Numeric	Admissions
Cumulative incidence of infectious disease hospital admissions	Cumulative incidence of infectious hospital admissions	Quantitative	Numeric	Admissions
Cumulative incidence of respiratory infectious hospital admissions	Cumulative incidence of respiratory infectious hospital admissions	Quantitative	Numeric	Admissions
Cumulative incidence of hospital admissions due to documented COVID-19	Cumulative incidence of hospital admissions due to documented COVID-19	Quantitative	Numeric	Admissions
Cumulative incidence all-cause and infectious intensive care admission	Cumulative incidence all-cause and infectious intensive care admission	Quantitative	Numeric	Nights
Cumulative incidence of intensive care admission due to	Cumulative incidence all-cause and infectious intensive care admission	Quantitative	Numeric	Nights

Variables	Definition	Type	Scale	Domain
documented COVID-19 infection				

Statistical methods

The responsible for statistical analyses in the consortium will be [name] affiliated with the University of Southern Denmark.

Data analysis:

Data will be reported quantitatively. All analyses will be performed from the intention-to-treat principle. Missing data on background variables will be dealt with by multiple imputation. Final data analysis will begin when the last participant in the multicentric RCT has completed the follow-up period. The primary endpoint, work absenteeism due to illness, will be reported as the total number of sick days with standard deviation. Total days of absenteeism will be analysed using a Bayesian negative binomial regression with a fixed effect for BCG, hospital, professional category, age, enrolment week and number of average workdays per week. The brm function from the R package "brms" will be used for fitting the negative binomial model. The effect will be reported as a relative risk with 95% confidence interval (CI). Please refer to section interim analysis for type-1 error control and power.

Similar regression models will be used for secondary endpoints. Cumulative incidence outcomes will primarily be analysed using Cox Proportional Hazard Regression.

Continuous baseline characteristics will be reported as means with the standard deviation or medians with the inter-quartile range, as appropriate. Categorical baseline characteristics will be reported as count and percentage. No statistical testing for baseline characteristics will be reported.

Please refer to the Data Analysis Plan for more details.

Interim analysis

Every month, an interim analysis will be conducted for each study site and of the combined dataset. Interim analyses will start after the 200th participant has been recruited across the two sites. The primary endpoint will be analysed as described above. The Bayesian model yields a posterior distribution of the relative risk (RR). The posterior probability of the superiority hypothesis ($RR < 1$) will be calculated. If during any of the interim analyses, the posterior probability of superiority is > 0.995 , a conclusion is reached, and the trial will be stopped.

Monthly, the following secondary endpoints will be reported from the sites: hospital admissions, and deaths.

IMPLEMENTATION

Inception

The study will begin with an inception meeting to be held in Cape Verde or virtually, depending on travel and quarantine recommendations at the time. Besides administrative issues, the meeting will address:

a) Strengthening Health Care Workers knowledge on Personal Protective Measures through provision of leaflets with detailed information on reasoning the use, the best practices, and the common pitfalls to avoid getting infected by COVID-19 or any other transmissible pathogens (when dealing with endemic highly transmissible diseases and/or future outbreaks, epidemics or pandemics). The leaflets will be developed based on best evidence available by members of consortium and will be handed-out to all health care workers working at the inclusion sites.

b) Short course on Fundamentals of Epidemics and Pandemics for Health Care Workers based in hospitals with limited resources. The course will cover best available knowledge on epidemiological characteristics of epidemics and pandemics and impart abilities/skills and attitudes to deal with epidemics and pandemics based on lessons learned from previous epidemics and pandemics in last 100 years, including strategies and interventions that are possible to implement for adequate containment and mitigation of epidemics and pandemics. We expect to develop the curriculum for the training and implement in all study sites. The initial training will be for 20 to 25 participants who will be trained in order to themselves be trainers and therefore replicate to their fellow colleagues along the time in their own Districts/Regions and elsewhere in their respective countries;

c) Short course on fundamentals of clinical research and RCT management - Training of research staff will include obtaining a certification in good clinical practice (GCP) and in the appropriate field procedures for all researchers involved in the study. GCP is an international ethical and scientific quality standard for designing, conducting, recording and reporting clinical trials, whose principles help assure the safety, integrity, and quality of clinical trials. The GCP training aims to ensure that the rights, safety, and well-being of human subjects are protected and that clinical trials are conducted in accordance with approved plans with rigor, and that data with integrity derived from clinical trials is reliable. GCP certification will be done online. Several certified online courses are currently available. We will prefer those recommended by the NHI.

See also study management, monitoring and quality control and Gantt chart.

Study setting

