Primarily a descriptive analysis will be performed of all information contained in the two study groups (BCG and placebo). All variables will be analysed, one by one, to know their distribution. Background factors will be summarised by counts (percentages), means (standard deviation) or medians (interquartile range) as appropriate. Proportions will be compared using the chi-square test - χ^2 test or Fisher's Exact test (categorical variable) or Student's t-test or Mann-Whitney test (quantitative variable) according to the distribution of variables. Statistical significance was set at the 5% level (two-tailed tests) and 95% confidence intervals (95%CI) for the estimates.

The endpoints variables (table 1) will be analyzed using univariate analysis (Logrank test) and Multivariate analysis (Cox Proportional Hazard Regression, or Cox Regression), stratified by the block randomization variables gender (male/female) and occupational group (doctors/ nurses/other) in addition to site. Covariates will be tested in the model univariate, and only those that were associated with the outcome at a significance level of at least 20% will be retained in a possible multivariate model. A significance level (p-value) of less than 0.05 and its respective confidence intervals (CI) will be used.

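### The section cited for type I error control gives only a per-look 0.995 rule; the stopping dataset, prior, number of looks and final threshold are left open

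*Protocol*

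**What the plan says.** Under Statistical methods, the protocol's Data analysis text specifies a Bayesian negative binomial model for days of absenteeism, reported as a relative risk with a 95% interval. It then says "Please refer to section interim analysis for type-1 error control and power" and, for the rest, "Please refer to the Data Analysis Plan for more details".

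The Interim analysis section contains the following:

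- Timing and data: "Every month, an interim analysis will be conducted for each study site and of the combined dataset".
- Start: "Interim analyses will start after the 200th participant has been recruited across the two sites".
- Rule: "If during any of the interim analyses, the posterior probability of superiority is" above 0.995, the trial stops with a conclusion.

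The protocol's Sample size section plans "for a mean absence of 4 days (80% power and alpha 0.05", without saying whether alpha is one- or two-sided.

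The SAP (Statistical analysis) repeats the Bayesian model and adds monthly reporting of absenteeism by arm to the DSMB. SAP section 3 calls the study adaptive and lets follow-up duration depend on the accumulating data. SAP section 6.1 says "Statistical significance was set at the 5% level (two-tailed tests" and, in the paragraph on the Table 1 endpoints, which include absenteeism, "A significance level (p-value) of less than 0.05 and its respective confidence intervals (CI) will be used". SAP Table 4 has columns for a 95% CI and a p-value from the Bayesian model of absenteeism. The available SAP text does not repeat the 0.995 rule.

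**The concern.** The cross-reference promises error control and power, and the section it points to gives neither. Four inputs that decide the error rate are open:

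- **Dataset.** With two sites there are three analyses a month. The stopping sentence can mean any month or any of the three datasets. On the second reading, one site can end the whole trial.
- **Prior.** None is stated for the log relative risk.
- **Looks.** No number or maximum is given.
- **Final criterion.** No posterior threshold is given. The only level in view is 5%, with no allowance for the interim looks.

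The DSMB cannot apply the rule without choosing a reading, and nobody can check afterwards that the error was held. The abstract says the interim results are meant to inform policy-makers, so a false stop would have consequences beyond the trial.

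**Working it through.** **The plan's own figure.** The only design figure to reproduce is 1050 participants for 80% power. Inputs from the protocol's Sample size section: means 5 and 4 days, SD 5, alpha 0.05, 5% loss.

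- Per arm, two-sided: 2 × (1.960 + 0.842)² × 5² / 1² ≈ 393. Total 786; 786 / 0.95 gives 828.
- At 1050 with 5% loss: 1050 × 0.95 / 2 = 498.75 per arm, and power is 88.5%.

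So 1050 is not the 80% figure from these inputs, but it errs on the safe side. No overall type I error is stated, so there is no such figure to reproduce.

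**Benchmark.** Alpha 0.05 (protocol) read with the SAP's two-tailed wording gives 2.5% in the benefit direction.

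**Simulation set-up.**

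- From the documents: 998 evaluable (1050 less 5%), 1:1 allocation, mean 5 and SD 5 over 6 months in both arms, monthly looks from the 200th recruit.
- Count model: gamma-Poisson with shape k from 25 = 5 + 25/k, so k = 1.25.
- Site split: 525/525 (SAP, Trial design), or 800/250 (protocol Table 2 gives Mozambique 100 + 150).
- Assumed, because not stated: accrual over 3 to 18 months (8 to 20 interims), a 4-month later start in Mozambique in some scenarios, and a N(0, s²) prior on log RR.
- Posterior z = (estimate / SE) × √(s² / (s² + SE²)). A look stops the trial if this exceeds 2.576 in the direction of benefit.
- Size: 13 null scenarios of 10,000 trials (Monte Carlo SE about 0.2 points at 5%), and a second run of 5 scenarios of 40,000.

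**Result: probability of falsely concluding benefit.**

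| Rule | Near-flat prior | s = 0.5 | s = 0.3 | s = 0.2 |
|---|---|---|---|---|
| Any site or combined can stop, interims only | 4.9-6.2% | 3.7-4.9% | 2.5-3.6% | 1.4-2.2% |
| The same plus final 95% interval | 6.1-7.6% | 4.9-6.1% | 3.8-4.8% | 2.6-3.4% |
| Combined only, interims only | 1.9-2.5% | 1.6-2.2% | 1.2-1.7% | 0.8-1.2% |
| The same plus final 95% interval | 3.4-4.1% | 3.1-3.8% | 2.7-3.3% | 2.2-2.6% |

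On the site reading with a near-flat prior, 59-73% of false interim stops occur where a site crosses and the combined data do not.

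**Why the prior helps little at the end.** At full data, SE² of log RR = (2 / 499) × (5/5)² = 0.00401. With s = 0.3 the shrinkage factor is √(0.09 / 0.09401) = 0.978, and with s = 0.2 it is √(0.04 / 0.04401) = 0.953. A sceptical prior mainly restrains the early looks, where SE is larger, and barely changes the final interval.

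**Cross-checks (flat prior).**

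- A Gaussian independent-increment simulation (200,000 runs, equally spaced looks) for 6 / 12 / 18 looks gives: combined only with 0.995 at every look, final included, 1.8 / 2.5 / 3.1%; combined with an unadjusted final test, 3.5 / 4.0 / 4.4%; site or combined, 4.4 / 6.1 / 7.2%; site or combined with the final test, 5.7 / 7.2 / 8.2%.
- A separate negative binomial simulation (12,000 runs, 10 to 16 looks) gives 2.3-2.6%, 3.7-4.3%, 5.6-7.0% and 6.8-8.1% for the same four rules.
- If the three hospitals in protocol Table 2 count as sites (76/10/14%), the Gaussian site-stopping error is 5.9 / 8.5 / 9.9%.

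**The case against.** **The rule holds on one reading.** If only the combined data can stop the trial, the interims stay within 2.5%, and one clarifying sentence would settle that part. This stands: the 0.995 threshold is not the error.

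**The final test is inferred.** The SAP's two-tailed sentence follows tests on background factors, and its p-value sentence closes a paragraph on Cox models. The 95% interval and Table 4 can be read as reporting formats. If 0.995 also applied at the final analysis of the combined data, error would be 1.8-3.1% (Gaussian) or 2.3-2.6% (negative binomial). This is fair, and it makes the rows with a final interval conditional. But no text says 0.995 applies at the end, and the only criteria in view for absenteeism are unadjusted.

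**The benchmark is inferred.** Against one-sided 5%, site stopping at the interims is only borderline (4.9-6.2%, near-flat prior). With a final one-sided 5% test, error is 8.0-9.7% if a site can stop and 5.7-6.5% if only the combined data can.

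**The size depends on assumptions.** One late-start scenario (18-month accrual, near-flat prior, 4,000 trials) gave 7.3% for site stopping, and 5.0% when site looks with fewer than 100 recruits were ignored. The upper end is therefore not sharp.

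**A meta-analysis follows.** The protocol describes a platform meta-analysis, run after a first significant result and excluding that trial, before any recommendation to offer BCG. This softens the consequence. It does not correct this trial's own conclusion, and the interim result is made public. The protocol also says that all trials are recommended to continue if the meta-analysis does not confirm the effect. That must be reconciled with the stop at 0.995.

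**Some text was not available.** A part of the protocol after the management organogram and the opening of the SAP could not be read, so a prior or final threshold could be stated there. The section cited for error control is complete as read, so the cross-reference fails regardless.

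**Conclusion.** The concern holds. It is certain that the cited section contains no overall error control and no power, and that the stopping dataset is ambiguous. In the available text, no prior, number of looks or final threshold is stated.

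The size is conditional. With a near-flat prior, the literal reading in which a site can stop the trial gives roughly two to three times the 2.5% benchmark: 4.9-6.2% from the interims and 6.1-7.6% with the final 95% interval. The cross-checks run somewhat higher. On the combined-only reading, the excess appears only when an unadjusted final interval is added (3.4-4.1%). A strongly sceptical prior (s = 0.2) brings combined-only error with the final interval to 2.2-2.6%, but site stopping with the final interval still gives 2.6-3.4%.

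These figures rest on the assumed prior, accrual time and site start lag, on the inferred 2.5% benchmark, and on reading the final 95% interval as a decision rule.

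**What to change.** 1. In the protocol's Interim analysis section, name the trigger, for example: *Only the posterior from the combined dataset can stop the trial; site-level results go to the DSMB as description.* If site stopping is wanted, raise its threshold by simulation.
2. Put the same rule, the prior on log RR and the look schedule in the SAP's Statistical analysis text, beside the DSMB sentence.
3. For the primary endpoint, replace the unadjusted 5% reading (SAP section 6.1 and Table 4) with one final posterior threshold. Calibrate it together with the interim threshold, under the actual prior and all looks, including those already held, to keep 2.5% in the benefit direction. A statistician who has not seen results by arm should do this.
4. Report the simulated error and power in the Interim analysis section, so that the cross-reference is true.

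Illustrations, to be replaced by the trial's own calibration:

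| Rule | False-benefit error or final threshold needed | Power (5 vs 4 days, SD 5 in both arms) |
|---|---|---|
| Combined only, 0.999 interim, 0.98 final | 2.1-2.5% near-flat; 1.8-2.2% at s = 0.3 | 85-87% near-flat; 83-86% at s = 0.3 |
| Combined only, 0.995 interim | final threshold of 0.986-0.995 near-flat; 0.979-0.983 at s = 0.3 | 80-81% with a 0.99 final |
| Site stopping kept, 0.999 on all three datasets, 0.99 final | 1.8-2.6% near-flat | 79-81% |

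The unadjusted combined-only rule has about 87-89% power, so the first option loses about 2-3 points and stays above the planned 80%. The cost is wording in both documents and one simulation, with no added participants. Inclusions began in December 2020 and the protocol is dated January 2022, so looks may already have taken place. The change may also need ethics approval as an amendment, and should state when it was made relative to the looks.
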